8.2 Sample Size and Power Considerations

It was determined that a sample size of 100 subjects per treatment group would detect a significant difference in proportion of PASI-75 and IGA responders from Baseline to Week 24 between each dose group of PPC-06 and placebo group, assuming a 15% response rate for the placebo group and 45% for PPC-06 at Week 24. To provide sufficient evidence of treatment effect, both PASI and IGA based response rate have to be rejected at the same significance level. The hypothesis testing for the 3 dose groups will be conducted sequentially from high to low dose; therefore, the 2-sided Type I error rate from a chi-squared test remains at the 0.05 level. Assuming 50% dropout rate, about 100 subjects per treatment arm will be randomized to get approximately 50 completers in each treatment arm. The total sample size of 400 subjects will yield at least 84% power for hypothesis testing of the co-primary endpoints of a difference in PASI-75 and IGA responders from Baseline to Week 24 between PPC-06 doses and placebo.

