## 7. SAMPLE SIZE DETERMINATION

It was determined that a sample size of 100 subjects per treatment group would detect a significant difference in proportion of PASI-75 and IGA responders from Baseline to Week 24 between each dose group of PPC-06 and placebo group, assuming a 15% response rate for the placebo group and 45% for PPC-06 at Week 24. To provide sufficient evidence of treatment effect, both PASI and IGA based response rate must reject at the same significance level. The hypothesis testing for the three dose groups will be conducted sequentially from high to low dose (600 mg BID, 400 mg BID and 400 mg QD); therefore, the 2-sided Type I error rate from a chi-squared test remains at the 0.05 level. Assuming 50% dropout rate, about 100 subjects per treatment arm will be randomized to get approximately 50 completers in each treatment arm. The total sample size of 400 subjects will yield at least 84% power for hypothesis testing of the co-primary endpoints of a difference in PASI-75 and IGA responders from Baseline to Week 24 between PPC-06 doses and placebo.

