## 9. HANDLING OF MISSING DATA

All imputations specified in this section will be performed for the Double-Blind Treatment and titration Period only; the Post-treatment Follow-Up Period data will be analyzed as observed.

For the analyses of the co-primary endpoints (PASI-75 and IGA), multiple imputation (MI) will be the primary imputation method. The modified non-responder imputation (m-NRI) and last observation carried (LOCF) method will be used as sensitivity analyses.

Details of the imputation methods are as following:

- **MI:** Missing data will be imputed using multiple imputations, a simulation-based approach where missing values are replaced by multiple Bayesian draws from the conditional distribution of missing data given the observed data and covariates, creating multiple completed data sets. These completed datasets can then be analyzed using standard analysis methods. MI will be implemented for all subjects with missing data, included those who used rescue medications or discontinued due to unsatisfactory therapeutic effect.

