The imputation of missing post-baseline BSA, PSSI final score, NAPSI, and NRS scores will be performed using a similar method as described for PASI. The imputation of missing post-baseline PP PGA scores will be performed using a similar method as described for IGA. A pre-specified seed number of 132138 will be used in all imputation procedures. No imputation will be done to the health-related quality of life endpoints or safety endpoints.

- **Observed cases (OC)**: No imputation will be performed, only observed values will be analyzed.
- **m-NRI (response endpoint only)**: Subjects who used rescue medications or discontinued due to unsatisfactory therapeutic effect are considered as treatment failures (i.e., non-responder) for all time points after the initiation of rescue medications or subject discontinuation. For example, if a subject discontinued due to lack of efficacy, all visits

after the last planned visits will be imputed to non-responders. If a subject used rescue medication during the study, all visits after the start of the rescue medication will be imputed to non-responders regardless if the subject had an assessment or not. Other subjects with missing data will be kept as missing (i.e., no imputation). Discontinuation due to unsatisfactory therapeutic effect will be identified by discontinuation reason = "Other" with a comment "lack of efficacy" on the eCRF.

- **LOCF:** The last observed value will be carried forward for any subsequent missing values. Baseline values will not be carried forward.

A summary of the imputation methods for all efficacy endpoints is shown below:

Endpoint	Analysis Population	Imputation Methods
PASI-75 at Week 24	FAS	MI, m-NRI, LOCF, OC
	PP	m-NRI
IGA score of clear or almost clear at Week 24	FAS	MI, m-NRI, LOCF, OC
	PP	m-NRI
Change from Baseline and percent change from Baseline in PASI Total Score by Visit	FAS	MI, LOCF, OC
	PP	OC
PASI-50 and PASI-75 by Visit	FAS	MI, m-NRI, LOCF, OC
	PP	m-NRI
IGA score of clear or almost clear by Visit	FAS	MI, m-NRI, LOCF, OC
	PP	m-NRI
Change from Baseline and percent change from Baseline in BSA by Visit	FAS	MI, LOCF, OC
	PP	OC
Change from Baseline in NPSI by Visit	FAS	MI, LOCF, OC
	PP	OC
Change from Baseline in PSSI by Visit	FAS	MI, LOCF, OC
	PP	OC
Change from Baseline in PP PGA by Visit	FAS	MI, LOCF, OC
	PP	OC
Change from Baseline in NRS by Visit	FAS	MI, LOCF, OC
	PP	OC
Time to PASI-75	FAS	OC
Time to achieving an IGA score of clear or almost clear	FAS	OC
QIDS-SR 16	FAS	OC

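### With 50% dropout assumed, no planned co-primary analysis counts tolerability dropouts as failures by rule, and none tests departure from missing at random

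*SAP*

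**What the plan says.** Protocol 8.2 and SAP 7 size the trial on heavy loss: "Assuming 50% dropout rate, about 100 subjects per treatment arm will be randomized to get approximately 50 completers in each treatment arm". The effect is planned "assuming a 15% response rate for the placebo group and 45% for PPC-06 at Week 24".

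SAP 9 (methods and summary table), SAP 12.8.1 and the table list in SAP 16 give the full set of Week 24 co-primary analyses:

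- **MI (primary, FAS).** Missing scores are imputed separately by arm from baseline BMI and earlier scores, whatever the reason for dropout, including rescue use and lack of efficacy.
- **m-NRI (sensitivity, FAS; supportive, PP).** Rescue users and subjects who stopped for lack of efficacy are non-responders from that point. For everyone else: "Other subjects with missing data will be kept as missing (i.e., no imputation". Lack of efficacy is recognised only from a discontinuation reason of Other with a matching comment.
- **LOCF (sensitivity, FAS).** "The last observed value will be carried forward for any subsequent missing values"; baseline is not carried forward.
- **OC (FAS).** No imputation. The table titles in SAP 16 also label this a sensitivity analysis.

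SAP 11.4 admits to Visits 3 to 8 only scores taken on drug or within 15 days of the last dose. SAP 8 limits the FAS to subjects with at least one post-dose efficacy assessment. Neither document contains full non-responder, delta-adjusted, tipping-point or reference-based imputation.

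**The concern.** Both documents give unresolved GI intolerance and protocol safety criteria as examples of why a subject would leave early. Protocol 5.4 requires permanent discontinuation for low lymphocyte counts, among other findings. Permanent discontinuation leads to the early termination visit, so Week 24 outcomes off drug are generally not collected. Tolerability dropout is therefore foreseeable, and it may be informative about Week 24 response.

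The question a reader of the results will ask is what happens if those subjects are not responders at Week 24. MI answers with an outcome learned almost entirely from on-drug scores in the same arm. m-NRI and OC do not answer it. LOCF answers with the last score, good or bad. If all of them agreed, the study report could call the result robust without that question having been put.

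**Working it through.** **1. Reproduce the stated power.** Inputs from SAP 7: 15% and 45%, about 50 completers per arm, two-sided 0.05, both endpoints required.

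Power per endpoint = Φ{(0.30 − 1.96·SE₀)/SE₁}, with SE₀ = √(2·0.30·0.70/50) = 0.0917 and SE₁ = √[(0.15·0.85 + 0.45·0.55)/50] = 0.0866. This gives Φ(1.39) = 0.918. For two endpoints treated as independent, 0.918² = 0.842, which matches the stated 84%. With n = 100 per arm the joint figure would be 99.5%. The design thus rests on completer rates, with about 50 of every 100 subjects lacking a Week 24 value.

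**2. A subject who stops for intolerance, without rescue, and has no Week 24 value:**

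| Analysis | Handling |
|---|---|
| MI | Imputed from own-arm, essentially on-drug, data |
| m-NRI | Left missing |
| OC | Dropped |
| LOCF | Responder if last score was a response, otherwise non-responder |

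**3. Full non-responder imputation, 50% dropout in each arm.** Active 0.50 × 45% = 22.5%; placebo 0.50 × 15% = 7.5%; difference 15 points. With n = 100 per arm, power is 0.849 per endpoint and 0.849² = 0.721 jointly.

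**4. Unequal dropout.** The documents give no dropout by arm, so these are assumptions. Completer rates stay at 45% and 15%, a 30-point difference throughout.

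| Dropout, active/placebo | Rates | Difference | Joint power |
|---|---|---|---|
| 50%/40% | 22.5% vs 9.0% | 13.5 points | 56.1% |
| 50%/30% | 22.5% vs 10.5% | 12.0 points | 39.6% |
| 60%/40% | 18.0% vs 9.0% | 9.0 points | 21.2% |
| 60%/30% | 18.0% vs 10.5% | 7.5 points | 10.8% |

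**5. LOCF at equal 50% dropout.** Let a and p be the proportions of active and placebo dropouts who were responders when last seen (assumed; not in the documents). Rates are 22.5% + 50%·a and 7.5% + 50%·p.

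| a/p | Rates | Difference |
|---|---|---|
| 20%/5% | 32.5% vs 10.0% | 22.5 points |
| 10%/10% | 27.5% vs 12.5% | 15.0 points |
| 10%/15% | 27.5% vs 15.0% | 12.5 points |

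LOCF can fall above, at or below the full non-responder result.

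**6. m-NRI.** If a share s of dropouts in each arm is for rescue or lack of efficacy (assumed), 50(1 − s) per 100 stay missing: 50, 40, 25 and 12.5 for s = 0, 0.2, 0.5 and 0.75. The rates are 22.5/(50 + 50s) and 7.5/(50 + 50s). At s = 0.2 this is 37.5% vs 12.5% (25 points); at s = 0.5, 30% vs 10% (20 points).

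No figure for MI can be derived, because it depends on the dropouts' earlier scores.

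**The case against.** This is a Phase 2 trial with a prespecified primary method, three alternative handlings and a per-protocol analysis. Which further stress test to add is partly a matter of preference. Full non-responder imputation is itself a fixed extreme, since it also fails subjects who simply missed the Week 24 visit. At equal dropout it does not overturn the planned effect: 22.5% against 7.5% with 100 per arm gives z = 0.15/0.0505 = 2.97, and the odds ratio moves from 4.64 in completers to 3.58. Those points stand. They argue for adding analyses, not for replacing the existing ones.

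A reader might go further and infer three things that the documents do not support:

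- **That every planned analysis leans towards active drug.** LOCF fails each dropout whose last score was a non-response, and step 5 shows that its direction depends on unknown last-seen rates.
- **That m-NRI leaves most dropouts missing.** No split by reason is given. This is true only if fewer than half are rescue or lack-of-efficacy cases.
- **That dropout falls mainly on active drug.** SAP 7 assumes about 50 completers in each arm; intolerance is only an example of a reason.

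Two smaller qualifications also hold. A tolerability dropout who had used rescue is a failure under m-NRI. A subject whose last dose was on Day 140 or later can have an observed Week 24 value, because that window opens at Day 155 and admits scores up to 15 days after the last dose.

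None of this supplies the missing analysis. LOCF is a different assumption from missing at random, but it is a single fixed one and does not show how large a departure would change the conclusion.

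**Conclusion.** The omission is real. The planned analyses neither count tolerability dropouts as non-responders by rule nor vary the missing-at-random assumption in a structured way, so their agreement would not establish robustness. At the plan's own rates with equal 50% dropout, counting every dropout as a failure halves the difference from 30 to 15 points and lowers joint power from about 84% to about 72%. If dropout were 10 to 30 points higher on active, the difference would be 13.5 to 7.5 points.

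These figures assume independent endpoints, unchanged completer rates and, for the unequal cases, dropout splits that the documents do not give. They show the room for disagreement between methods. They do not predict the result or show that the primary analysis is biased.

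**What to change.** In SAP 9 and 12.8.1, before unblinding, add for both co-primary endpoints:

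1. **Full non-responder imputation** of every missing Week 24 response, on all randomized treated subjects. Run on the FAS, it would still omit those who left before any post-dose efficacy assessment.
2. **A delta-adjusted tipping-point MI or a placebo-reference MI.**

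LOCF, m-NRI and OC can stay as supportive analyses. The primary analysis, sample size and conduct do not change.

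The cost is programming and additional tables that may be less favourable. Placebo-reference MI needs a new imputation run, because the current SAS code imputes separately by treatment arm. The report should describe full non-responder imputation as a conservative extreme, since it also fails administratively missing visits.

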## 10. INTERIM ANALYSIS

The overall response rate for PASI-75 and IGA success at Week 16 and 24, will be reported when 50, 100 and 200 subjects complete the treatment period. The interim will be performed on blinded data using the m-NRI, OC and LOCF imputation method. All subjects in full analysis set (FAS) that have completed Week 24 assessments or early terminated by the interim data cut date will be included in the analysis. No formal shell is required.

## 11. DATA CONVENTIONS FOR ANALYSIS

### 11.1 General Statistical Principles

All statistical tests will be performed at the unadjusted 0.05 (two-sided) level of significance.

All observed and derived variables (e.g., change from baseline, percentage change from baseline, response status) used in the summaries of analyses will be presented in by-subject listings. Descriptive statistics will be used to provide an overview of the efficacy and safety results. For categorical parameters, the number and percentage of subjects in each category will be presented. The denominator for percentage will be based on the number of subjects appropriate for the purpose of analysis. For continuous parameters, descriptive statistics will include number of subjects, mean, standard deviation (SD), median, minimum, and maximum.

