8. STATISTICAL METHODS AND DETERMINATION OF SAMPLE SIZE STATISTICAL AND ANALYTICAL PLANS

8.1 General Considerations for Data Analysis

The methodology presented in this section represents a brief overview of the statistical methods that will be fully detailed in the statistical analysis plan (SAP). The SAP will be finalized before the database is locked and unblinded. Any changes to the methods described in the final SAP will be described and justified in the clinical study report.

Study sites will be pooled into analysis centers for the efficacy analyses. The composition of pooled analysis centers will be finalized before the database is locked and unblinded.

All statistical analyses will be performed using SAS statistical software (Version 9.2 or above). Statistical significance will be tested at the 2-sided 5% level. Subgroup analyses (eg, prior biologic use) may be performed.

Data collected in this study will be presented using summary tables, figures, and subject data listings. Summary tables will present data by treatment group and, if applicable, by time of collection. Continuous variables will be summarized using descriptive statistics, specifically the mean, median, standard deviation, minimum and maximum. Categorical variables will be summarized by frequencies and percentages. Figures will be used to support the presentation of certain data.

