8.7.4 Control of Multiplicity

For the primary efficacy analysis (PASI-75 and IGA), each of the PPC-06 doses will be compared with placebo separately, sequentially from high to low dose to maintain the Type-I error rate. Therefore, no adjustments for multiplicity will be performed.

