### **12.8.2 Secondary Efficacy Analyses**

All secondary efficacy analyses will be performed on the FAS and PP populations.

The following categorical secondary efficacy endpoints will be summarized using the number and percentage of subjects within each category for each treatment group. A same logistic regression model as used for the primary endpoint will be performed. Each PPC-06 group will be compared to placebo separately as described in the primary analysis.

- Proportion of subjects who achieve PASI-50 and PASI-75 by visit in the Double-Blind Treatment Period
- Proportion of subjects who achieve an IGA score of clear or almost clear by visit in the Double-Blind Treatment Period

The observed values and change from baseline in PP PGA will be summarized as categorical endpoint using frequency counts and percentages. The change from baseline in severity categories will be compared between treatment groups using a Wilcoxon rank sum test.

The following continuous secondary efficacy endpoints will be summarized descriptively and analyzed using an Analysis of Covariance (ANCOVA) including factors for treatment, baseline

BMI, and pooled analysis center. Each PPC-06 group will be compared to placebo separately. The least square mean (LSM) difference, along with the 95% CI and p-value will be reported.

- Change from Baseline and percent change from Baseline in total PASI Score by visit in the Double-Blind Treatment Period
- Change from Baseline and percent change from Baseline in percent of affected BSA by Visit in the Double-Blind Treatment Period
- For applicable subjects, change from baseline in NAPSI of the target fingernail at Weeks 12, 16 and 24
- For applicable subjects, change from baseline by visit in PSSI in the Double-Blind Treatment Period
- Change from Baseline and percent change from Baseline in pruritus NRS score by Visit in the Double-Blind Treatment Period

The following time to event variables will be analyzed using the Kaplan-Meier (KM) method. Subjects who have not achieved treatment response by the last visit or discontinue the study will be censored at their last visit. The mean, 25th, 50th, and 75th percentile time to achieving a treatment success will be reported; log-rank test will be performed for the comparison between each PPC-06 arm and placebo.

- Time to achieving PASI-75 response
- Time to achieving IGA 0 or 1

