	PPC-06 400 mg QD (N=XX)	PPC-06 400 mg BID (N=XX)	PPC-06 600 mg BID (N=XX)	Placebo (N=XX)
Pooled Analysis Site (Clinical Sites)				
A01 (112 113 114)				
N	XX	XX	XX	XX
Response Rate [1]	XX.X	XX.X	XX.X	XX.X
A02 (101 102 105)				
N	XX	XX	XX	XX
Response Rate [1]	XX.X	XX.X	XX.X	XX.X
XXX				
N	XX	XX	XX	XX
Response Rate [1]	XX.X	XX.X	XX.X	XX.X

<include all pooled *Analysis Site*>

Note: PASI=Psoriasis Area and Severity Index. PASI-75 Response is defined as achieving a reduction of 75% or greater from Baseline.

[1] Average PASI-75 response rate over 50 imputed datasets.

Generated on XX/XX/XX:XXXX by XXXXX / Uses: XXXX / Reference: Listing XXXX

<Repeat for>

Table 14.2.1.5.2: Analysis of Co-Primary Efficacy Outcome  
IGA Treatment Success Rate at Week 24 by Visit and Analysis Sites  
Full Analysis Set, Multiple Imputation

*Programming note: modify the Note accordingly for the definition of IGA treatment success*

Table 14.2.2.1.1.1: Analysis of Secondary Efficacy Outcome  
 Change from Baseline in Total PASI Score by Visit  
 Double-Blind Treatment Period  
 Full Analysis Set, Multiple Imputation

	PPC-06 400 mg QD (N=XX)	PPC-06 400 mg BID (N=XX)	PPC-06 600 mg BID (N=XX)	Placebo (N=XX)
Week 8				
Change from baseline [1]				
N	XX	XX	XX	XX
Mean	XX.X	XX.X	XX.X	XX.X
Analysis of Covariance (ANCOVA) [2]				
LSM (SE)	XX.X (XX.X)	XX.X (XX.X)	XX.X (XX.X)	XX.X (XX.X)
LSM, 95% CI	XX.X, XX.X	XX.X, XX.X	XX.X, XX.X	XX.X, XX.X
LSM Difference (SE), PPC-06 vs. Placebo	XX.X (XX.X)	XX.X (XX.X)	XX.X (XX.X)	
95% CI	XX.X, XX.X	XX.X, XX.X	XX.X, XX.X	
p-value	X.XXXX	X.XXXX	X.XXXX	

<Repeat for other visits: Week 12, Week 16, Week 20, and Week 24>

Note: PASI=Psoriasis Area and Severity Index, SE=Standard Error.

[1] Average based on 50 imputed datasets.

[2] ANCOVA model includes treatment as factor, baseline BMI and pooled analysis centers as covariates.

Generated on XX/XX/XX:XXXX by XXXXX / Uses: XXXX / Reference: Listings XXXX

<Repeat for>

Table 14.2.2.1.1.2: Analysis of Secondary Efficacy Outcome  
Percent Change from Baseline in Total PASI Score by Visit  
Double-Blind Treatment Period  
Full Analysis Set, Multiple Imputation

Table 14.2.2.1.2.1: Analysis of Secondary Efficacy Outcome  
Change from Baseline in Total PASI Score by Visit  
Double-Blind Treatment Period  
Full Analysis Set, LOCF

	PPC-06 400 mg QD (N=XX)	PPC-06 400 mg BID (N=XX)	PPC-06 600 mg BID (N=XX)	Placebo (N=XX)
Baseline				
N	XX	XX	XX	XX

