*Programming note: modify the Note accordingly for the definition of OC*

Table 14.2.2.2.5: Analysis of Secondary Efficacy Outcome  
PASI-50 Response Rate by Visit in the Double-Blind Treatment Period  
PP Population, m-NRI

*Programming note: modify the Note accordingly for the definition of m-NRI*

Table 14.2.2.3.1: Analysis of Secondary Efficacy Outcome  
PASI-75 Response Rate by Visit  
Double-Blind Treatment Period  
Full Analysis Set, Multiple Imputation

	PPC-06 400 mg QD (N=XX)	PPC-06 400 mg BID (N=XX)	PPC-06 600 mg BID (N=XX)	Placebo (N=XX)
Week 8				
N	XX	XX	XX	XX
% [1]	XX.X	XX.X	XX.X	XX.X
Logistic Regression [2]				
Log (Odds Ratio) (SE), PPC-06 vs. Placebo	XX.X (XX.X)	XX.X (XX.X)	XX.X (XX.X)	
Odds Ratio	XX.X	XX.X	XX.X	
Odds Ratio 95% CI	XX.X, XX.X	XX.X, XX.X	XX.X, XX.X	
p-value [3]	X.XXXX	X.XXXX	X.XXXX	

<Repeat for other visits: Week 12, Week 16, Week 20>

Note: PASI=Psoriasis Area and Severity Index; SE=Standard Error; CI=Confidence Interval. PASI-75 Response is defined as achieving a reduction of 75% or greater from Baseline.

[1] Average PASI-75 response rate over 50 imputed datasets.

[2] Logistic model includes treatment group, baseline BMI, and pooled analysis center as factors.

[3] p-value is for null hypothesis that the combined log (Odds Ratio) equals 0.

Generated on XX/XX/XX:XXXX by XXXXXX / Uses: XXXX / Reference: Listing XXXX

[programming note: no need to present Week 24 in this table]

Table 14.2.2.3.2: Analysis of Secondary Efficacy Outcome  
PASI-75 Response Rate by Visit  
Double-Blind Treatment Period  
Full Analysis Set, LOCF

	PPC-06 400 mg QD (N=XX)	PPC-06 400 mg BID (N=XX)	PPC-06 600 mg BID (N=XX)	Placebo (N=XX)
Baseline				
n / N (%)	XX/XX (XX.X)	XX/XX (XX.X)	XX/XX (XX.X)	XX/XX (XX.X)
Week 8				
n / N (%)	XX/XX (XX.X)	XX/XX (XX.X)	XX/XX (XX.X)	XX/XX (XX.X)
Logistic Regression [1]				
Odds Ratio, PPC-06 vs. Placebo	XX.X	XX.X	XX.X	
Odds Ratio 95% CI	XX.X, XX.X	XX.X, XX.X	XX.X, XX.X	
p-value	X.XXXX	X.XXXX	X.XXXX	

<Repeat for other visits: Week 12, Week 16, Week 20>

Note: PASI=Psoriasis Area and Severity Index; CI=Confidence Interval; LOCF=Last Observation Carried Forward. PASI-75 Response is defined as achieving a reduction of 75% or greater from Baseline. n = Number of responders at each visit. N = Number of subjects available for analysis at each visit.

[1] Logistic model includes treatment group, baseline BMI, and pooled analysis center as factors.

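### Secondary efficacy p-values are tested at unadjusted two-sided 0.05 for three doses at up to five visits, with no key visit, endpoint order, gate or nominal label, so their family-wise error is severely inflated

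*SAP*

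**What the plan says.** The general rule in SAP 11.1 is "All statistical tests will be performed at the unadjusted 0.05 (two-sided) level of significance", and Protocol 8.1 has "Statistical significance will be tested at the 2-sided 5% level".

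Multiplicity is addressed only for the co-primaries. Both PASI-75 and IGA success at Week 24 must be significant for a dose, and testing is "conducted sequentially from high to low dose (600 mg BID, 400 mg BID and 400 mg QD" (SAP 7; the same rule is in SAP 12.8.1). After describing this sequence for the primary analysis, Protocol 8.7.4 concludes: "Therefore, no adjustments for multiplicity will be performed". Neither document has a corresponding statement for secondary endpoints.

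SAP 12.8.2 then sets out the secondary tests:

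- PASI-50, PASI-75 and IGA response by visit use the primary logistic model. "Each PPC-06 group will be compared to placebo separately as described in the primary analysis".
- PASI, BSA, NAPSI, PSSI and pruritus NRS use ANCOVA. "The least square mean (LSM) difference, along with the 95% CI and p-value will be reported".
- PP PGA uses a Wilcoxon test, and the two times to response use log-rank tests of each dose against placebo.

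The table shells start at Week 8 and continue "<Repeat for other visits: Week 12, Week 16, Week 20, and Week 24>". For PASI-75 by visit they add "programming note: no need to present Week 24 in this table", because Week 24 is the co-primary; the IGA shells do the same. NAPSI is tested at Weeks 12, 16 and 24.

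By contrast, SAP 12.8.3 keeps quality of life descriptive, and SAP 12.8.4 says the subgroup analyses involve no formal testing.

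**The concern.** The SAP disclaims formal testing where it wants to, for subgroups, and does not do so for secondary efficacy. The rule in SAP 11.1 therefore applies there at full strength. Nothing names a key secondary endpoint or visit, ranks the endpoints, or makes a dose's secondary results depend on that dose having passed both co-primaries.

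As written, a dose that fails the co-primaries could still be reported as statistically significant on some secondary endpoint at some visit, and the plan would supply the rule for saying so. Secondary objective 1 includes efficacy on psoriasis symptoms. Protocol 2.3 also describes the earlier Phase 2 study's key secondary endpoints in terms of statistical significance, so a reader may well do the same here. At stake is what the trial may conclude outside its co-primaries, and any dose choice that leans on those results.

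**Working it through.** **The plan's own figure.** The documents give no family-wise rate for secondary endpoints. The figure that can be checked is the power of at least 84% in SAP 7. Inputs: 50 completers per arm, 15% versus 45%, two-sided 0.05.

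- Null SE = √(2 × 0.30 × 0.70 / 50) = 0.0917
- Alternative SE = √((0.15 × 0.85 + 0.45 × 0.55) / 50) = 0.0866
- Power per endpoint = Φ((0.30 − 1.96 × 0.0917) / 0.0866) = Φ(1.39) = 0.918
- Both endpoints, taken as independent: 0.918² = 0.842

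This reproduces 84%, so two-sided 0.05 for the co-primaries is consistent with the stated power.

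**Count of secondary comparisons**, from SAP 12.8.2 and the shells, using one imputation method per endpoint:

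| Endpoint | Visits |
|---|---|
| PASI change; PASI percent change | 5 + 5 |
| PASI-50 | 5 |
| PASI-75; IGA success (Week 24 excluded) | 4 + 4 |
| BSA change; BSA percent change | 5 + 5 |
| NAPSI | 3 |
| PSSI; PP PGA | 5 + 5 |
| NRS change; NRS percent change | 5 + 5 |
| Time to PASI-75; time to IGA 0/1 | 1 + 1 |
| Total cells | 58 |

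58 cells × 3 doses = 174 p-values against placebo.

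**Expected false positives if no dose has any effect.** 174 × 0.05 = 8.7 in either direction, and 174 × 0.025 = 4.35 favouring drug. These expectations hold at any correlation.

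**Chance of at least one.** If the tests were independent: 1 − 0.95^174 = 0.9999 in either direction and 1 − 0.975^174 = 0.988 favouring drug. They are not independent. Doses share a placebo arm, visits repeat, and several endpoints overlap. Two null simulations with assumed correlations give a range.

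Model A: one common correlation among the 58 cells within an arm, z = (dose − placebo)/√2, rejection if |z| > 1.96, 40,000 trials.

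| Common correlation | Either direction | Favouring drug |
|---|---|---|
| 0.3 | 99% | 76% |
| 0.5 | 94% | 59% |
| 0.9 | 44% | 22% |

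Model B: correlation 0.5 between doses (shared placebo, equal arms), separate endpoint and visit correlations, at least 0.9 for each change and percent-change pair, 20,000 trials per setting. The last column asks what happens if the high-to-low order applies within each cell. A false claim must then start with 600 mg BID, so only its 58 tests count.

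| Endpoint / visit correlation | Either direction | Favouring drug | Favouring drug, dose order applied |
|---|---|---|---|
| 0 / 0.5 | 0.994 | 0.903 | 0.614 |
| 0.5 / 0.7 | 0.941 | 0.614 | 0.353 |
| 0.85 / 0.85 | 0.641 | 0.338 | 0.165 |

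The dose-order column comes from Model B only; a uniform correlation of 0.9, as in Model A, would give less than its lowest entry.

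**The case against.** Four parts of the opposing case stand.

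- **No secondary claim is planned.** This is a Phase 2 trial. The co-primary objectives are to demonstrate efficacy; the secondary ones are to assess it. No passage defines secondary success or says that a dose failing the co-primaries will be called effective. SAP 11.1 openly describes its level as unadjusted.
- **Near certainty is not supported.** A reader might infer from 174 tests that a false efficacy finding is almost guaranteed. That follows only from independence, or from counting results that favour placebo. Efficacy claims need results favouring drug, where the range is far wider and rests on assumed correlations.
- **Some order may already exist.** A reader might infer that no hierarchy reaches the secondary endpoints, and that the SAP dropped the link to the primary analysis for continuous ones. SAP 12.8.2 does omit the cross-reference there, but Protocol 8.7.2 has it for both types. SAP 1 says the SAP does not repeat every protocol definition, and SAP 13 lists only PP PGA as a change. Whether the cross-reference imports the dose order, or only the pairwise comparison with placebo, is unclear.
- **Larger counts are not larger error.** Over every listed imputation method and population there are 129 × 4 + 39 × 5 + 6 = 717 p-values, but these re-analyse the same comparisons. Still, SAP 9 names MI as primary only for the co-primaries, so the count of 174 assumes a choice the SAP does not make for secondary endpoints.

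None of this supplies a key visit, an order across endpoints, a gate or a nominal label. Even with the dose order applied, the chance of a false result favouring drug in Model B stays well above the 2.5% of a single test.

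**Conclusion.** The point holds for secondary efficacy p-values. With 174 dose-versus-placebo comparisons at unadjusted two-sided 0.05, the family-wise error is severely inflated: 8.7 expected false positives under a global null, 4.35 favouring drug. The chance of at least one favouring drug is roughly 22% to 90%, about 60% at moderate correlation, or about 17% to 61% if the dose order carries over. The counts come from the documents. The probabilities rest on a null effect for every dose on every endpoint and on correlations assumed here.

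A reader might also infer that the primary conclusion is compromised. It is not: requiring both co-primaries and testing doses in sequence controls that error. This is an inexpensive improvement that should be made, and it does not count against the primary analysis.

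**What to change.** Replace the SAP 11.1 sentence with a statement to this effect:

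> Only the two co-primary endpoints at Week 24 (FAS, MI), tested in the order 600 mg BID, 400 mg BID, 400 mg QD, are confirmatory at two-sided 0.05. Testing stops at the first dose for which either co-primary has p ≥ 0.05. All other p-values, including those for secondary endpoints, other visits, other populations and other imputation methods, are nominal, and no claim of statistical significance rests on them.

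Add the nominal label as a footnote to Tables 14.2.2.x. State whether the cross-reference to the primary analysis carries the dose order to secondary endpoints.

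If a formal secondary claim is wanted, pre-specify a short fixed order at Week 24 (FAS, MI), tested only for doses that passed both co-primaries. Choosing Week 24 as the key visit is not enough by itself. Even with the dose order, 12 secondary outcomes would remain as entry tests, and 1 − 0.95^12 = 0.46 if independent. The order must run as one chain across endpoints and doses; separate chains at 0.05 for each dose would not hold the overall rate at 5%.

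The cost is SAP wording and a table footnote, with no new data or programs. The nominal label changes no estimate or p-value. The sponsor gives up calling secondary results statistically significant outside the named order.
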